4.1.3 RANDOMIZATION

Considering the bilateral cross-over study design, participants will either wear Proclear 1 day or clariti elite lenses in both eyes first and then switch over to the alternate lens type. The order of lenses will be determined using a randomization schedule.

A randomization schedule will be generated for the study by CORE's data management team and provided to the research assistants. Study investigators will remain masked to the randomization schedule until the study is completed and the database is locked.

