4.2 STUDY POPULATION

4.2.1 SAMPLE SIZE CALCULATION

Sample size: The target sample size for this study is 30 participants to be randomized and to wear both lens types. This target was determined based on the sample size calculation below:

Based on previous data for "lens handling for removal" which showed a standard deviation of the difference between means of 18 points (0-100 scale), a minimum sample size of 28 is required to detect a paired difference between groups of 10 units on a 0-100 scale with 80% power and alpha 0.05 in a two-tailed t-test.

Therefore, in this study, a maximum of 30 participants to be randomized and wear both lens types.

11. Have undergone refractive error surgery or intraocular surgery;
12. Are a member of CORE directly involved in the study.

* For the purposes of this study, active ocular disease is defined as infection or inflammation which requires therapeutic treatment. Mild (i.e. not considered clinically relevant) lid abnormalities (blepharitis, meibomian gland dysfunction, papillae), corneal and conjunctival staining and dry eye are not considered active ocular disease. Neovascularization and corneal scars are the result of previous hypoxia, infection or inflammation and are therefore not active.

* Any potential exclusion will be reviewed with the Lead Investigator or Principal Investigator prior to final decision making.

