4.3 STUDY MATERIALS

4.3.1 LENSES

If deemed eligible after screening, participants will wear two different contact lenses bilaterally on the same day, in a randomized sequential order: clariti elite and Proclear 1 day.

The control lens is the commercially available, daily disposable Proclear 1 day, manufactured by CooperVision, Inc. The test lens is the frequent replacement (monthly) clariti elite, manufactured by CooperVision, Inc.

The test lenses are not approved for sale in Canada and therefore and ITA (Investigational Testing Authority) will be sought from Health Canada prior to them being used in the study. The control lens, Proclear 1 day, is commercially available in Canada.

Lenses will be worn for a period of approximately 90 minutes each during the study visit only.

Table 1: Study lens specifications

	Test	Control
Lens name	clariti elite	Proclear 1 day
Manufacturer	CooperVision	CooperVision
HC licence #	N/A- investigational	106827
Material	somofilcon A	omafilcon A
EWC (%)	56%	60%
Dk/t (-3.00)	86	28
Base Curve (mm)	8.6	8.7
Diameter (mm)	14.2	14.2
Sphere Power (D)	-1.00 to -6.00 (0.25 steps)	-1.00 to -6.00 (0.25 steps)
Replacement schedule	Monthly replacement	Daily disposable

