4.4.2 SCREENING (V1)

A documented informed consent process will be conducted with all participants prior to their enrolment in the study and prior to any data collection or measurements.

All participants who sign the informed consent letter will be assigned a study ID number. The investigator will determine participant eligibility using the inclusion and exclusion criteria. Ineligible participants will be discontinued from the study. The procedures to be performed are outlined below.

Visit procedures:

1. The participant is expected to attend the screening visit with their habitual glasses NOT having worn their habitual contact lenses and/or used any rewetting/tear drops on the study day.
2. The participant will be required to read and sign an Informed Consent Form prior to enrollment. When the participant has signed the consent form, the participant will be considered enrolled in the study.
3. Participant demographics and medical history (age, sex, medical conditions, medications, allergies).
4. Contact lens history (habitual lens information and wearing habits).

14. Slit lamp biomicroscopy including Fl staining to assess ocular health.
15. The investigator will confirm that the participant meets the eligibility specifications set out in the inclusion criteria and exclusion criteria and is eligible to continue in the study.

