4.4.4 LENS 2 WEAR PERIOD (V3)

The Lens 1 Wear Period (V2) will be immediately followed by Lens 2 Wear Period (V3) on the same day. This visit will involve the alternate lens type, i.e. the study lens type not yet worn.

Visit procedures:

1. The participant will be assigned the second pair (lens pair #2) of study contact lenses, which will be selected according to the randomization table by unmasked study personnel.
2. The crossover lens pair #2 will be provided to participants in a manner, which does not unmask the participant or investigator, as described in Section 4.3.5.
3. Repeat steps 3-13 from V2 (section 4.4.3).
4. Subjective preference 5-point Likert between lenses for handling related to lens insertion/ removal and overall handling experience (binocular preference).

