11 STATISTICAL ANALYSIS AND DATA MANAGEMENT

11.1 STATISTICAL ANALYSIS

All study data will be analyzed by CORE at the University of Waterloo. Summary statistics will be produced (e.g. mean, standard deviation). Data analysis will be conducted using Statistica and / or SPSS, or other appropriate software. Descriptive statistics will be provided on information regarding baseline demographic variables (age, sex, refractive error distribution, etc.). Table 6 lists the primary outcome and other variables and anticipated statistical procedures. All data will be tested for normality of distribution using Shapiro-Wilk tests.

A binomial test will be used to analyze the results for the count data of subjective preferences. The number of “no preference” responses will be evenly distributed to the two options on the basis they would be equally likely to choose either.

The critical alpha level for statistical significance will be set at 0.05.

For assessments conducted for each eye separately, the right eye will be used for analysis. If a general difference is found (paired t-test / Wilcoxon matched pairs) between OD and OS, a comment will be provided.

All participants who completed the study will be used in the analysis, unless exclusion agreed with the sponsor based on protocol deviation or adverse event information. In the event of missing data, individual data points will not be extrapolated from the collected data.

Table 6: Outcome variables and anticipated statistical procedures

Variable	Analysis	Statistical test
Subjective ratings, Primary outcome: binocular subjective rating of the ease of lens application to eye	Descriptive and other statistics	Mean, Median, Standard Deviation, Minimum, Maximum, Frequency count
	Effect of study treatment (comparison between study lenses)	Paired t-test Wilcoxon matched pairs test Friedman

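### Table 6 analyses a randomised-order crossover with paired tests that use neither period nor sequence; a period-adjusted comparison costs little when the sequences are near equal and protects power and the estimate

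*Combined protocol and SAP*

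**What the plan says.** Section 4.1.3 sets the design: "Considering the bilateral cross-over study design, participants will either wear Proclear 1 day or clariti elite lenses in both eyes first and then switch over". It adds that "The order of lenses will be determined using a randomization schedule". The text available gives no allocation ratio, blocking or balance rule.

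The two periods run back to back. Section 4.4.4 says "The Lens 1 Wear Period (V2) will be immediately followed by Lens 2 Wear Period (V3) on the same day", and section 4.3.1 says "Lenses will be worn for a period of approximately 90 minutes each during the study visit only". Under section 4.4.2 participants arrive "NOT having worn their habitual contact lenses and/or used any rewetting/tear drops on the study day".

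Section 4.2.1 bases the sample size on a paired two-sided t-test with an SD of 18 points: "a minimum sample size of 28 is required to detect a paired difference between groups of 10 units on a 0-100 scale" for 80% power at alpha 0.05. It then sets "a maximum of 30 participants to be randomized and wear both lens types".

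For the primary outcome (ease of applying the lens to the eye, 0-100), Table 6 gives the between-lens tests as "Paired t-test Wilcoxon matched pairs test Friedman". No period, sequence or order term, and no check for one, appears in the text available. Section 11.1 analyses completers, less any exclusions agreed with the sponsor.

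**The concern.** The outcome is a self-rated manual task done twice in one day, and the two occasions differ. In the text available, the V2 insertion is the first time the participant rates insertion in the study, with no lens worn earlier that day. The V3 insertion follows a complete cycle of opening, applying, rating, wearing and removing the first pair. Practice, fatigue or re-anchoring on the scale could move the second rating either way.

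If ratings shift by P points from V2 to V3, the test-minus-control difference contains +P for participants who wear the test lens second and -P for those who wear it first. The paired tests pool these differences. With equal sequences P cancels from the mean but inflates the estimated SD, so the test becomes conservative and loses power. With unequal sequences P does not fully cancel, and the remainder is reported as a lens effect. Planned power is only a little above 80% and enrolment is capped, so lost precision cannot be recovered by adding participants.

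**Working it through.** **Inputs.** From section 4.2.1: difference 10, SD of the paired difference 18, two-sided alpha 0.05, N = 28 minimum and 30 maximum. Assumed, because the documents do not give them: P = 0, 5, 10 or 15 points; SD 18 within each sequence; sequence splits of 15:15, 18:12 and 20:10.

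**Step 1. Reproduce the plan's figure.** Paired t power from the noncentral t, with df = N-1 and noncentrality 10/(18/√N):
- N = 27: 79.4%
- N = 28: 80.9%
- N = 30: 83.7%

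The minimum of 28 is correct for a paired t-test with no period shift.

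**Step 2. Model.** For participant i, d_i = δ + P·s_i + e_i, where s_i = +1 if the test lens is worn second and -1 if first, and e_i has SD 18.
- *Paired estimator:* the mean of all d_i. Its bias in a given trial is P(n1-n2)/N, where n1 is the number wearing the test lens second. At 15:15 the expected sample variance is 18² + P²·N/(N-1). For P = 10 that is 324 + 100 × 30/29 = 427.4, an SD of 20.7. For P = 5 and 15 the SD is 18.7 and 23.6.
- *Adjusted estimator:* (m1+m2)/2, where m1 and m2 are the sequence means of d_i, with pooled within-sequence variance, df = N-2 and SE = √[(18²/4)(1/n1 + 1/n2)]. It does not depend on P.

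**Step 3. Equal sequences, 15:15, N = 30** (simulation, 200,000 trials per scenario):

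| P | Paired power | Adjusted power | Paired type I error | Paired mean 95% CI half-width |
|---|---|---|---|---|
| 0 | 84% | 84% | 5.0% | 6.7 |
| 5 | 82% | 84% | 4.2% | 6.9 |
| 10 | 75% | 84% | 2.6% | 7.7 |
| 15 | 64% | 84% | 1.1% | 8.7 |

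The adjusted half-width is 6.7 throughout and its type I error is 5%. At N = 28 (14:14) with P = 5, 10 and 15, paired power is 79, 72 and 60%, against 81% adjusted.

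**Step 4. Unequal sequences, N = 30, P = 10.**
- 18:12: bias = 10 × 6/30 = 2.0 points. Paired type I error is 5.3%, and paired power is about 55% or 90% depending on direction. Adjusted power is 82%.
- 20:10: bias = 10 × 10/30 = 3.3 points. Paired type I error is 11%, and paired power is 40% or 95% depending on direction. Adjusted power is 79%, with 5% error.

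The higher paired figure in each pair reflects bias toward the true effect and is not a real gain. If randomisation were simple, the chance of 18:12 or worse is 2 × P(X ≤ 12) = 0.36, and of 20:10 or worse 2 × P(X ≤ 10) = 0.10, with X binomial (30, 0.5).

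**Step 5. Averaged over simple 1:1 randomisation.** The paired test has no bias and type I error of 4.9 to 5.0% at every P. Its power is 84, 81, 73 and 61%, against 82% adjusted.

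**Step 6. If the SD of 18 already contains the shift.** The within-sequence SD is then √(324-P²) = 17.3, 15.0 and 9.9 for P = 5, 10 and 15. At 15:15 paired power is 84, 88 and 95%; adjusted power is 86, 94 and over 99%.

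**Step 7. Rank tests at 15:15** (6,000 trials each). Signed-rank power is 82, 79, 72 and 60% for P = 0, 5, 10 and 15. A rank-sum test on period differences gives about 80%.

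**The case against.** The strongest reply is that no error has been shown. Randomised order makes the paired test unbiased on average with correct type I error, and the sample size and the planned test agree with each other. No P is documented. The large losses need P of 10 or 15, which equals or exceeds the lens difference the study is sized for, in habitual wearers for whom inserting a lens is not new. At P = 5 and 15:15, paired power is still 82%. The SD of 18 may come from data that already contained a period shift, in which case planned power is not at risk. The bias scenarios also need unequal sequences. At 20:10 with no shift, adjustment itself takes power from 83.7% to 79.1%, below the 80% target. Finally, some visit steps are redacted and Table 6 calls its procedures anticipated, so an order check could sit in text that cannot be seen.

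Most of this stands and limits the weight of the point: it rules out calling the trial invalid or underpowered. It does not justify leaving period out. The sponsor will report one trial with one realised split, and even a balanced schedule can become unequal through the completer analysis set and agreed exclusions. If the SD already contains P, adjustment still gains about 2, 7 and 5 percentage points. The SD of 18 comes from ratings of lens removal, so it says little about a period effect on insertion. The primary-outcome row of Table 6 is legible and contains no such term.

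**Conclusion.** The concern holds as a point of efficiency and robustness that should be addressed before analysis. The planned tests are valid on average but leave the result exposed to a V2-to-V3 shift. At 15:15 and N = 30 the power loss is about 2, 8 and 20 percentage points for P = 5, 10 and 15. At 18:12 and 20:10 with P = 10, the lens estimate in that trial is off by 2.0 and 3.3 points.

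These sizes rest on an assumed P and on a within-sequence SD of 18. The figures for how often the sequences would be that unequal also assume simple randomisation. If P is near zero, or the SD of 18 already includes it, planned power is not threatened and the benefit is smaller. Period adjustment does not remove carryover from the first lens to the second.

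**What to change.** In Table 6, make the primary analysis the period-adjusted 2×2 crossover comparison: a two-sample t-test of within-participant period differences (V2 minus V3) between the two lens-order sequences. The lens effect is half the difference in sequence means, signed as test minus control, reported with its 95% CI. For complete pairs this is equivalent to a mixed model with lens, period and sequence as fixed effects and participant as a random effect. If the data are non-normal, use the Wilcoxon rank-sum test on period differences by sequence. The paired t-test can stay as a supportive analysis. Stating in section 4.1.3 how the schedule balances the two sequences would keep the cost of adjustment low.

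The change is wording only, since lens order is already known from the schedule. It uses one degree of freedom (28 instead of 29). With no period shift, power goes from 83.7% to 83.6% at 15:15, 82.1% at 18:12 and 79.1% at 20:10. Adjustment breaks even at P of about 1 point at 15:15, and about 3 to 4 points averaged over simple randomisation. The rank-sum version costs about 2 percentage points when there is no shift.

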11.2 DATA MANAGEMENT

11.3 COMMENTS ON SOURCE DOCUMENTS

Data analysis will not be conducted on comments which have been recorded in the source documents. Only relevant and applicable comments will be included in the final report as deemed necessary by the lead investigator.

12 PROTOCOL TRAINING

All study personnel will be required to complete training prior to their involvement in the study. Records of training will be kept at CORE.

[figure not shown]
13 STUDY MONITORING

The Sponsor will ensure site qualification of the investigative site has been completed prior to conducting the clinical study in order to ensure that the site facility is adequate, personnel are qualified and resources are satisfactory.

CORE will provide status reports to the study sponsor by email on a regular basis.

Status reports will include:

- The number of participants screened, enrolled, and randomized (i.e. assigned a study ID number), discontinued and completed.
- Details of protocol deviations.
- Reports of unintended events.

Consent documentation will be reviewed by a person not involved in the consent process. To improve data integrity, data entry will be conducted by one person and a second person will visually compare the data entry to the source documents.

All adverse events and protocol deviations will be reviewed by the Lead Investigator and reported to the sponsor. Documentation of any serious adverse events and major protocol deviations will be reviewed by the Head of Clinical Research and the PI.

14 STUDY MANAGEMENT

14.1 STATEMENT OF COMPLIANCE

This clinical study was developed in accordance with the ethical principles in the Declaration of Helsinki, with the ICH guidelines for Good Clinical Practice (GCP) (ICH E6 R2), with ISO 14155:2020 Clinical Investigation of Medical Devices for Human Subjects, with the University of Waterloo's Guidelines for Research with Human Participants and with the Tri-Council Policy Statement: Ethical Conduct for Research Involving Humans, 2nd Edition.

- Declaration of Helsinki
- ICH E6 - International Council for Harmonisation of Technical Requirements for Pharmaceuticals for Human Use Guidelines for Good Clinical Practice
- Tri-Council Policy Statement: Ethical Conduct for Research Involving Humans – TCPS 2 (2022)
- <https://uwaterloo.ca/research/office-research-ethics/research-human-participants>

14.3 CLINICAL TRIAL REGISTRATION

This study will be registered on clinicaltrials.gov.

14.4 PROTOCOL DEVIATIONS

Protocol deviations are unanticipated or unintentional changes to a study after it has received prior sponsor approval and ethics clearance. Protocol deviations can be major or minor.

14.4.1 MAJOR PROTOCOL DEVIATIONS

Major protocol deviations may impact the research protocol, information consent document or other study materials, usually cannot be anticipated ahead of time and are often necessary to ensure the safety and welfare of the participants.

The following are examples of protocol deviations that must be reported to the ORE:

- Changes in procedures initiated to eliminate immediate risks/hazards to participants;
- Enrollment of participants outside the protocol inclusion/exclusion criteria whether agreed to or not by the sponsor;
- Device / intervention errors (i.e. incorrect contact lens(es) dispensed);

- Inadvertent deviation in specific research intervention procedures or timing of the research intervention which could impact upon the safety or efficacy of the study-related intervention or upon the experimental design;
- Information consent documentation violations: no documentation of informed consent; incorrect version of, or incomplete, informed consent documentation used.

14.4.2 MINOR PROTOCOL DEVIATIONS

Protocol deviations caused by or which originate with research participants are considered minor, and normally are not reported to the ORE unless these result in increased risk to the participant(s). The following are examples of protocol deviations that are considered minor and do not require reporting to the ORE:

- Logistical or administrative aspects of the study;
- Inadvertent deviation in specific research intervention procedures or timing of the research intervention which would not impact upon the safety or efficacy of the study-related intervention or upon the experimental design (i.e., missing a measurement during a session that is not considered critical for the study).

14.4.3 REPORTING AND DOCUMENTING PROTOCOL DEVIATIONS

Major protocol deviations must be reported to the ORE within 7 days of the deviation occurring (or its discovery) using the Protocol Deviation Report Form 107 (PDRF). Information from the PDRF is provided to the Clinical Research Ethics Committee (CREC) at the next monthly meeting. All deviations shall be reported to the study sponsor within two working days.

All protocol deviations (major and minor) occurring during the study will be documented on a protocol deviation form and included in the final report.

14.6 STUDY PARTICIPANT RECORDS

Study participant records will be completed to comply with GCP guidelines. Records will contain:

- Unique study acronym and/or code;
- Participant ID;
- Date enrolled;
- Confirmation by investigator that participant met eligibility criteria;
- Confirmation that participant received a signed and dated copy of informed consent;
- Exit date;
- Investigator's signature confirming study exit.

15 REPORT

A report will be sent to the sponsors according to terms described in the study contract.
